9.3.4 Lab Parameters

Lab parameters with value below the lower limit of quantification (LLOQ) or above the upper limit of quantification (ULOQ) will be imputed as the LLOQ or ULOQ value, respectively.

9.4 Outliers

Observations found to be due to data entry errors will be corrected by the study team before final database lock. Potential outliers that are not due to data entry error will be included in the primary analysis. The validity of any questionable values will be confirmed. No valid measurement will be purposely excluded from descriptive or inferential analyses. However, sensitivity analyses **excluding the outliers** may be conducted to evaluate the influence of extreme values in the data. These analyses will be documented in the clinical study report.

9.5 Distributional Characteristics

The assumptions underlying the parametric models analyzed for continuous data will be checked. In cases where residuals indicate marked departures from the assumptions, additional sensitivity analyses will be performed using transformations or alternate methods such as nonparametric or robust procedures.

9.6 Validation of Statistical Analyses

Programs will be developed and maintained, and output will be verified according to processes described in procedures or technical manuals about the "Configuration

Management of Statistical Analysis and Reporting Systems”, “Statistical Analysis and Reporting System Development and Validation”, and “Development of Statistical Analysis and Reporting Systems”.

Tables, figures, and listings will be produced with validated standard macro programs where standard macros can produce the specified outputs.

The production environment consists of Amgen-supported versions of The SAS System running on the Sun Solaris operating system. Because it is common for multiple versions of SAS to be available during the study period, the SAS version used to produce analyses will be documented in the validation documentation and the clinical study report.

10. Statistical Methods of Analysis

10.1 General Principles

The hypotheses will be tested and the romosozumab treatment effects will be estimated using statistical models and summary statistics.

For computation of change from baseline endpoints, baseline will be taken as the observation recorded just prior to first dose of IP. In the case where the protocol specifies multiple baseline measurements to be taken, the mean of the baseline records will be used for analysis.

All efficacy analyses will be performed by randomized treatment, regardless of actual treatment received.

Continuous variables will be summarized descriptively using mean, median, standard deviation, 25th percentile, 75th percentile, minimum, maximum, and the number of non-missing observations. Frequencies and percentages will be presented for nominal categorical variables.

10.2 Subject Accountability

The disposition of all randomized subjects will be tabulated by randomized treatment group. Subject enrollment and disposition for the number (%) of subjects randomized, successfully completing IP administration, completing the 6 month treatment period, and completing the 9 month study period will be included. The disposition of subjects will also include the number (%) of subjects who withdrew from the IP and their reasons for withdrawal, study completion, and the number of subjects who withdrew from study and their reasons for withdrawal.

10.3 Important Protocol Deviations

Important Protocol Deviations (IPDs) categories are defined by the study team before the first subject's visit and updated during the IPD reviews throughout the study prior to database lock. These definitions of IPD categories, sub-category codes and descriptions will be used during the course of the study. The final IPD list is used to produce the summary of IPDs table and the list of subjects with IPDs.

Eligibility deviations are defined in the protocol. A summary table and a list of deviations from eligibility criteria will also be generated.

10.4 Demographic and Baseline Characteristics

Subject demographic and baseline disease characteristics as listed below will be summarized by treatment group based on the FAS defined in [Section 7.1](#).

- demographics (race, sex, ethnicity, age at study entry [year], age groups [<65 , ≥ 65 to <75 , and ≥ 75])
- body composition (height [cm], weight [kg], BMI [kg/m²])
- BMD T-score at lumbar spine, total hip and femoral neck
- BMD (g/cm²) by machine type at lumbar spine, total hip and femoral neck
- bone turnover markers (CTX, P1NP)
- years since menopause (year)
- fracture history (Y/N) (**including historic fracture, historic fracture at age ≥ 45 , historic fracture at age ≥ 55 , time since the most recent fracture in months**)
- laboratory parameters (calcium corrected by albumin, phosphorus, **creatinine, estimated glomerular filtration rate (eGFR), eGFR [< 15 , 15 to < 30 , 30 to < 60 , 60 to < 90 , and ≥ 90 mL/min/1.73m²]**), serum 25 (OH) vitamin D level and iPTH)
- glucocorticoid use (Yes, No)
- substance use in the past 5 years including tobacco use (never, former, current); alcoholic beverages (none, ≤ 2 per day, ≥ 3 per day);
- baseline use of vitamin D (Yes, No)
- baseline use of calcium (Yes, No)
- parental hip fracture (Yes, No, Unknown)
- secondary osteoporosis (Yes, No)
- rheumatoid arthritis (Yes, No)
- **cardiovascular risk factors (age ≥ 75 , < 75], smoking history and other clinical history including hypertension, diabetes, cardiovascular disease, and hypercholesterolemia)**

The cardiovascular risk factors of history of hypertension, diabetes, cardiovascular disease, central nervous system vascular disorder and hypercholesterolemia will be identified based on the Medical & Surgical History eCRF based on MedDRA version 20.0 or later. The SMQ for Hypertension, the SMQ for Hyperglycaemia, and the SOC of Cardiac Disorders and Vascular Disorders will be used to identify preferred terms associated with hypertension, diabetes and cardiovascular disease, respectively. The Dyslipidaemia SMQ will be used to identify history of hypercholesterolemia, excluding terms associated with conditions of low cholesterol or increased high-density lipoprotein. The preferred terms utilized are listed in [Appendix 13.4](#).

Summary tables of prior and concomitant medication will also be generated by treatment group using FAS.

Subject demographic and history of cardiovascular risk factors will be summarized using all subjects in FAS.

10.5 Dose of Calcium Supplement and Vitamin D Loading Dose Administration at Baseline

Calcium supplement dose and Vitamin loading dose will be summarized by baseline vitamin D level (< 20 ng/mL, ≥ 20 ng/mL and ≤ 40 ng/mL, and > 40 ng/mL) and randomized treatment group.

10.6 Efficacy Analyses

All statistical testing will be 2-sided. The baseline value of BMD and machine type will be included in the statistical model for primary and secondary efficacy analyses. For each of the efficacy BMD endpoints (lumbar spine, total hip, and femoral neck at Month 6), descriptive statistics will be provided for **actual** values and percent change from baseline at post-baseline visit by machine type and visit.

10.6.1 Primary Analysis of Primary Efficacy Endpoint

The primary analysis to assess the percent change from baseline in lumbar spine DXA BMD at Month 6 will employ an ANCOVA model. The ANCOVA model will include treatment, baseline DXA BMD value as main effects. Additional covariates of machine type (Hologic or Lunar) and machine type by baseline DXA BMD value interaction will also be included in the model to adjust for the effect of machine type on baseline DXA BMD value. SAS procedure PROC MIXED is to be used to obtain the least squares means (LSM) point estimates of the percent change from baseline for each treatment

arm. Model based adjusted treatment difference of LSM with associated 95% CI and corresponding p-value will be presented. SAS code fragments are provided in Appendix 13.2.1.

Conclusion for the primary efficacy hypothesis of different efficacy of romosozumab compared with placebo at lumbar spine BMD at 6 months will be made using a 2 sided test with type 1 error rate of 0.05.

The primary analysis will use the BMD efficacy analysis set.

10.6.2 Primary Analysis of Secondary Efficacy Endpoints

For each of the secondary efficacy BMD endpoints (total hip and femoral neck percent change from baseline at Month 6), the analysis approach follows that specified in [Section 10.6.1](#).

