7.3.13 Dual-energy X-ray Absorptiometry

Bone density measurements will be performed by DXA. Only Lunar or Hologic bone densitometers will be allowed for the study. The same DXA machine must be used for all study procedures for a particular subject for the duration of the study. All DXA scans will be submitted to and analyzed by the central imaging vendor. A separate procedure manual provided by the central imaging vendor will give specific instructions for acquisition of scans as well as performance of Instrument Quality Control.

Bone density will be measured at the lumbar spine and proximal femur. DXA scans of the lumbar spine will be performed in duplicate (ie, subjects will be removed from the table in between scans). Lumbar spine scans must include L1 through L4. For proximal femur DXA scans, the left side should be used for all scans at all study visits. If the right side must be used (eg, due to implants) or is inadvertently used at baseline, then it must be used consistently throughout the study. If a subject fractures the hip that has been

scanned during the study up to the time of fracture, no further scans will be obtained for the affected location.

All DXA scan data will be submitted electronically to the central imaging vendor for analysis. Sites unable to submit data electronically can submit on compact disc or other media as specified in the DXA Procedural Manual, but electronic submission is preferred.

After analysis by the central imaging vendor, the study site may be asked to re-acquire a scan due to malpositioning or other technical reasons. The study site must comply with the requests from the central imaging vendor. Repeat scans must be performed as soon as possible after the request is received.

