10.4.2 Primary Analysis

The primary analysis will be performed after all subjects have had the opportunity to complete the month 6 visit.

The primary objective of the primary analysis is to evaluate the effect of treatment with romosozumab for 6 months compared with placebo on percent changes in BMD at the lumbar spine as assessed by DXA in South Korean women with osteoporosis. Formal statistical testing will be conducted to evaluate the following hypothesis: in South Korean women with osteoporosis, the mean percent change in lumbar spine BMD in subjects receiving romosozumab will be different to that of those receiving placebo at month 6.

Secondary objectives of the primary analysis include the evaluation of the effect of treatment with romosozumab compared with placebo on the following:

- Percent change from baseline in DXA BMD at the femoral neck and total hip at month 6

Exploratory objectives of the primary analysis include the evaluation of the effect of treatment with romosozumab for 6 months compared with placebo on the following:

- Percent changes from baseline in BTMs P1NP and CTX

For the exploratory objectives, all inferential statistics will be considered exploratory in nature.

Safety objectives of the primary analysis include the comparison of the safety and tolerability for 6-month treatment with 210 mg romosozumab QM to placebo in South Korean women with osteoporosis on the following:

- Subject incidence of adverse events, including Event of Interest (EOI)
- Changes from baseline in laboratory assessments (serum chemistry and hematology) and shifts from baseline to the worst value
- Changes from baseline in vital signs
- Incidence of subjects with anti-romosozumab antibodies

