10.5.2 Primary Efficacy Endpoint

The analysis to assess the percent change from baseline in lumbar spine DXA BMD at month 6 will employ an analysis of covariance (ANCOVA) model. The ANCOVA model will include treatment group, baseline value of BMD, machine type and interaction of baseline BMD value and machine type as independent variables. Summaries for the results will include least-squares means point estimates of the percent change from baseline for each treatment arm. The variance structure will allow for heterogeneity between treatments. The 2-sided 95% CI and associated p-value will be provided for the difference between the least-squares means for romosozumab and placebo.

Conclusions for the primary efficacy hypothesis of different efficacy of romosozumab compared with placebo at lumbar spine BMD will be made using a 2-sided test with

type 1 error rate of 0.05. The BMD efficacy analysis set will be used to for these analyses.

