10.5.3 Secondary Efficacy Endpoints

For the secondary efficacy BMD endpoints (total hip and femoral neck at month 6), the percent change from baseline in DXA BMD will employ an ANCOVA model. The ANCOVA model will include treatment group, baseline value of BMD, machine type and interaction of baseline BMD value and machine type as independent variables.

Summaries for the results will include least-squares means point estimates of the percent change from baseline for each treatment arm. The variance structure will allow for heterogeneity between treatments. The 2-sided 95% CI and associated p-value will be provided for the difference between the least-squares means for romosozumab and placebo. The BMD efficacy analysis set will be used for these analyses.

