10.6.3 Analyses of Exploratory Efficacy Endpoints

For P1NP and CTX, descriptive statistics will be presented by treatment group at each visit for both absolute values, change from baseline and the percent change from baseline values. Graphs depicting median and interquartile ranges by treatment group for percent change over time will be provided. The significance of the treatment difference for the percentage change from baseline at each visit will be assessed using a Wilcoxon Rank-Sum test. SAS code fragments are provided in Appendix 13.2.2.

The BTM efficacy analysis subset will be used for these analyses.

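### Do the total hip and femoral neck p-values need a gate, a testing order or a multiplicity adjustment?

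*SAP*

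**What the plan says.** For lumbar spine, Protocol 10.4.2 states that "Formal statistical testing will be conducted to evaluate the following hypothesis", and the hypothesis that follows names lumbar spine BMD only. Protocol 10.5.2 then gives the decision rule: "Conclusions for the primary efficacy hypothesis of different efficacy of romosozumab compared with placebo at lumbar spine BMD will be made" with a two-sided 5% test. SAP 10.6.1 repeats it: the conclusion "at lumbar spine BMD at 6 months will be made using a 2 sided test with type 1 error rate of 0.05".

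For total hip and femoral neck, Protocol 10.5.3 repeats the ANCOVA description and ends with the estimate and its p-value: "The 2-sided 95% CI and associated p-value will be provided for the difference between the least-squares means for romosozumab and placebo". It has no sentence about drawing conclusions at 0.05. SAP 10.6.2 is a single cross-reference to 10.6.1: "total hip and femoral neck percent change from baseline at Month 6), the analysis approach follows that specified in" that section.

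For the bone turnover markers, Protocol 10.4.2 adds a label: "For the exploratory objectives, all inferential statistics will be considered exploratory in nature". SAP 10.6.3 plans a between-group test for them, which "will be assessed using a Wilcoxon Rank-Sum test".

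No readable part of either document gives the hip sites a gate, an order, a split of alpha, an adjustment or a statement that none is made. SAP 11, the section for changes from the protocol's analyses, shows no text.

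**The concern.** Two p-values are reported next to a primary endpoint with a strict 5% rule, and their standing is not stated. Two features make this look like more than a missing word.

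- The SAP's cross-reference points to a section that contains the 0.05 conclusion rule, so a reader could take that rule to apply to each hip site as well.
- Protocol 10.4.2 labels the exploratory statistics as exploratory. It lists the secondary endpoints just above and gives them no label.

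The Amendment 2 rationale says the study supports registration in Korea. If a hip p-value fell below 0.05, a reader might ask whether it is a claim or a description. If both sites were treated as separate 5% claims, the error rate across the pair would exceed 5%. The order of listing does not help, because Protocol 10.1.1.2 puts femoral neck first and SAP 4.1.2 puts total hip first.

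**Working it through.** **1. Reproduce the plan's own figure.** Inputs from Protocol 10.2 and SAP 3.2: difference 6.6, SD 3.9, two-sided alpha 0.05, 30 per arm, 10% dropout (27 per arm).

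- SE at 27 per arm = 3.9 × √(2/27) = 1.061. Noncentrality = 6.6 / 1.061 = 6.22, df = 52. Power from the noncentral t = 99.998%.
- At 30 per arm, SE = 3.9 × √(2/30) = 1.007 and power = 99.9996%.

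The stated power of more than 99% reproduces. It concerns lumbar spine only; neither document gives a hip power, a hip SD or a hip difference from placebo.

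**2. Set the texts side by side.**

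| Item | Lumbar spine | Total hip, femoral neck |
|---|---|---|
| Efficacy hypothesis (Protocol 2.5, SAP 5) | stated | none |
| Formal test named (Protocol 10.4.2) | yes | listed for evaluation of the effect |
| 0.05 conclusion rule (Protocol 10.5.2, SAP 10.6.1) | yes, names this site | absent from Protocol 10.5.3 |
| Power statement (Protocol 10.2, SAP 3.2) | yes | none |
| Model, LS means, CI, p-value | yes | yes |

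The hip endpoints share the modelling and the reporting. Every confirmatory element belongs to lumbar spine alone.

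**3. Size of the error if the hip p-values were read as claims anyway.** With both hip nulls true and jointly normal estimates, the chance of at least one false positive is 1 − P(|Z₁| ≤ 1.96 and |Z₂| ≤ 1.96). At independence this is 1 − 0.95² = 0.0975. The documents give no correlation between the sites, so it is assumed over a range. A positive value is likely because both come from the same femur scan (Protocol 7.3.13: "Bone density will be measured at the lumbar spine and proximal femur").

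| Assumed correlation | 0 | 0.5 | 0.8 | 0.9 |
|---|---|---|---|---|
| Unadjusted | 0.0975 | 0.0907 | 0.0781 | 0.0704 |
| Holm, first step at 0.025 | 0.0494 | 0.0465 | 0.0402 | 0.0362 |

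If only one hip null is true, only one false positive is possible and the unadjusted chance is 5%. Over all three BMD sites with no effect anywhere, independence gives 1 − 0.95³ = 14.3%. That case requires no lumbar spine effect either, although Protocol 10.2 cites an earlier difference of 7.9 (95% CI 6.6 to 9.3).

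**4. Price of a formal procedure.** Effects are in SD units, 27 per arm, df 52. The effect detectable with 90% power is 0.899 SD at alpha 0.05 and 0.983 SD at alpha 0.025. For a true effect of 0.899 SD:

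- Holm, other site without effect: power at the affected site falls from 90% to about 84%.
- Holm, both sites at 0.899 SD: 89%, 88% and 87% per site at correlations 0, 0.5 and 0.8.
- Fixed sequence, both sites at 0.899 SD: the first site keeps 90%; the second has 81%, 83% and 86% at the same correlations.
- The lumbar spine gate costs almost nothing, since it is passed with probability 99.998% under the plan's assumptions.

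**The case for a change.** The best case for a change is that the supportive status of the hip p-values is inferred and never written down. The authors knew how to write such a label, since they wrote one for the exploratory objectives, and its absence for the secondary endpoints could be read as deliberate. With the SAP's cross-reference to a section that holds the 0.05 rule, a registration purpose, and a one-sentence remedy that costs nothing, a reviewer could reasonably ask for the sentence.

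What stands is that the label is missing. The rest is weaker.

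- The cross-reference imports an analysis approach, meaning the ANCOVA, the LS means, the interval and the p-value. The decision rule in SAP 10.6.1 names lumbar spine BMD and does not transfer to another site without rewording.
- Protocol 10.5.3 closely follows 10.5.2 yet leaves out the conclusion sentence, which points the same way.
- Supporting registration in Korea does not imply a hip claim, and neither document asks for one.
- The inflated error rate needs two things together: a claim reading that the text does not support, and no effect at either hip site. Protocol 2.4 reports a 2.9% rise in total hip BMD at six months on this regimen (95% CI 2.3% to 3.4%). That is a change from baseline and not a difference from placebo, but it makes the second condition unlikely.

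**Conclusion.** No change to the plan is needed. This is a gap that analysts fill sensibly. Followed as written, the plan gives one confirmatory conclusion at lumbar spine, controlled at two-sided 5% with power above 99%, and two hip estimates with unadjusted intervals and p-values that are read as supportive. A nominal label would alter no estimate, interval, p-value or primary conclusion. A gate with Holm or a fixed sequence would build a confirmatory hip claim that the documents do not ask for, at a cost in hip power that statisticians could fairly debate.

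The most that could be at stake is an error rate of 7.0% to 9.75% across the two hip sites, over assumed correlations from 0.9 down to 0, and only if both nulls are true and both p-values are treated as claims. Otherwise it is 5% or less.

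This rests on the readable text. The SAP's code fragments are withheld and some front matter was removed, but a testing hierarchy would be expected in the methods sections, which are readable. It also rests on the sponsor not intending a formal hip claim. If one were intended, a procedure fixed before the month 6 unblinding would be required, but nothing in the documents indicates that intention.

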10.6.3 Analyses of Exploratory Efficacy Endpoints

For P1NP and CTX, descriptive statistics will be presented by treatment group at each visit for both absolute values, change from baseline and the percent change from baseline values. Graphs depicting median and interquartile ranges by treatment group for percent change over time will be provided. The significance of the treatment difference for the percentage change from baseline at each visit will be assessed using a Wilcoxon Rank-Sum test. SAS code fragments are provided in Appendix 13.2.2.

The BTM efficacy analysis subset will be used for these analyses.

10.7 Safety Analyses

Safety data will be summarized by the actual treatment received in the treatment period (any subject randomized to placebo who incorrectly receives ≥ 1 dose of romosozumab will be analyzed as receiving romosozumab and any subject randomized to romosozumab who incorrectly only receives placebo doses will be analyzed as receiving placebo).

Safety data for the 6-months of treatment period and the 9-month study period will be summarized using safety analysis set defined in [Section 7.4](#).

10.7.1 Adverse Events

The Medical Dictionary for Regulatory Activities (MedDRA) version 20.0 or later will be used to code all AEs to a system organ class and a preferred term. AEs will be summarized in the 6-month treatment period and in the 9-month study period for all subjects who receive at least one dose of IP in the treatment period, ie, safety analysis

set. The subject incidence rates for the 9-month study period will include all events that occurred in the 6-month treatment period, and in addition, all events that occurred in the additional 3 month follow-up period. In addition, AEs reported between month 6 and month 9 (no treatment phase) will be listed by subject number and treatment received in the first 6 months.

All AE tables will be summarized by treatment group. The subject incidence of AEs will be summarized for all treatment emergent, serious, treatment related, serious treatment related, leading to withdrawal of IP, fatal, and of special interest. Subject incidence of special interest adverse events will also be summarized according to their categories.

Subject incidence of all treatment emergent, , serious, those leading to withdrawal of IP, related to IP adverse events will be tabulated by system organ class (SOC) and preferred term in descending order of frequency in the romosozumab arm. Fatal adverse events will be tabulated by preferred term in descending order of frequency in the romosozumab arm.

Disease related events (DRE) will be indicated in the AE listing and only tabulated with sufficient data.

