9. SAFETY DATA COLLECTION, RECORDING, AND REPORTING

9.1 Definition of Safety Events

9.1.1 Disease-related Events

Disease-related events are events (serious or non-serious) anticipated to occur in the study population due to the underlying disease. Fractures (serious or non-serious) are

anticipated to occur in the study population due to the underlying disease. Such events do not meet the definition of an adverse event unless:

- assessed to be more severe than expected for the subject's condition or
- if the investigator believes there is a causal relationship between the IP(s)/study treatment protocol required therapies and disease worsening.

If one of these criteria are met, the disease-related event must be reported as an adverse event or serious adverse event; otherwise, it will be reported as a disease-related event.

Disease-related events and/or disease-related outcomes that do not qualify as serious adverse events:

- An event which is part of the normal course of disease under study (eg, disease progression in oncology or hospitalization due to disease progression) is to be reported as a Disease Related Event.
- Death due to the disease under study is to be recorded on the Event CRF.

If the outcome of the underlying disease is worse than that which would normally be expected for the subject, or if the investigator believes there is a causal relationship between the IP(s)/study treatment protocol required therapies and disease worsening, this must be reported as an adverse event or serious adverse event.

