9.1.3 Serious Adverse Events

A serious adverse event is defined as an adverse event that meets at least 1 of the following serious criteria (unless it meets the definition of a disease-related event as defined in [Section 9.1.1](#)):

- fatal
- life threatening (places the subject at immediate risk of death)
- requires in-patient hospitalization or prolongation of existing hospitalization
- results in persistent or significant disability/incapacity
- congenital anomaly/birth defect
- other medically important serious event

A disease-related event is to be reported as a serious adverse event if:

- the subject's pre-existing condition becomes worse than what the investigator would consider typical for a patient with the same underlying condition, or
- if the investigator believes a causal relationship exists between the investigational medicinal product(s)/protocol-required therapies and the event,
- and the event meets at least 1 of the serious criteria above.

An adverse event would meet the criterion of "requires hospitalization", if the event necessitated an admission to a health care facility (eg, overnight stay).

If an investigator considers an event to be clinically important, but it does not meet any of the serious criteria, the event could be classified as a serious adverse event under the criterion of "other medically important serious event". Examples of such events could include allergic bronchospasm, convulsions, blood dyscrasias, DILI (see [Appendix A](#) for DILI reporting criteria), or events that necessitate an emergency room visit, outpatient surgery, or urgent intervention.

The criteria for grade 4 in the CTCAE grading scale differs from the regulatory criteria for serious adverse events. It is left to the investigator's judgment to report these grade 4 abnormalities as serious adverse events.

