9.2 Safety Event Reporting Procedures

9.2.1 Reporting Procedures for Disease Related Events

The investigator is responsible for ensuring that all disease-related events observed by the investigator or reported by the subject that occur after first dose of IP through the EOS visit, ET visit, or 30 days after the last dose of IP (whichever period is longer) are reported using the Event CRF. Additionally, the investigator is required to report a fatal disease-related event on the Event CRF.

Events assessed by the investigator to be related to the IP/study treatment/protocol-required therapies, and determined to be serious, require reporting of the event on the Event CRF.

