10.5.5.1 Adverse Events

For the 6-month treatment period, subject incidence of all treatment-emergent adverse events will be tabulated by system organ class and preferred term. Tables of fatal adverse events, serious adverse events, **events of interest (including positively adjudicated osteonecrosis of the jaw, positively adjudicated atypical femoral fracture, injection site reaction, and positively adjudicated serious cardiovascular adverse events)**, adverse events leading to withdrawal from IP or other

protocol-required therapies, and treatment-emergent adverse events will also be provided. Subject incidence of disease-related events and fatal disease-related events will be tabulated by system organ class and preferred term. The treatment-emergent adverse events in the overall 9-month study period (6-month treatment period followed by a 3-month follow-up period) will be summarized using the same approach as for the 6-month treatment period. In addition, adverse events reported between month 6 and month 9 (no treatment phase) will be listed by subject number and treatment received in the first 6 months.

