10.7.1.1 Events of Interest (EOIs)

Events of interest of hypersensitivity and malignancy will be identified using a narrow search/scope in standardized MedDRA queries (SMQ). Event of interest of hypocalcemia, injection site reaction, hyperostosis, and osteoarthritis will be identified using Amgen-defined MedDRA search strategies. Subject incidence rates of these events will be provided.

Adjudicated positive cardiovascular serious adverse events, adjudicated AEs of osteonecrosis of the jaw (ONJ) and atypical femoral fracture (AFF) will also be summarized as EOIs.

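### The SAP tabulates disease-related events, including ordinary fractures, only on an undefined condition where the protocol sets none; its exposure set and eGFR creatinine unit also need correcting (minor)

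*SAP*

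**What the plan says.** **Disease-related events.** Protocol 10.5.5.1 states: "Subject incidence of disease-related events and fatal disease-related events will be tabulated by system organ class and preferred term". It attaches no condition. The sentence names no period, but its paragraph opens "For the 6-month treatment period, subject incidence of all treatment-emergent adverse events will be tabulated". SAP 10.7.1 states: "Disease related events (DRE) will be indicated in the AE listing and only tabulated with sufficient data". It gives no event count, no time for the judgement and no one to make it, and it does not mention fatal DREs.

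What counts as a DRE matters here. In protocol 9.1.1, "Fractures (serious or non-serious) are" expected in this population because of the disease, and "Such events do not meet the definition of an adverse event unless" they are worse than expected for the subject or the investigator suspects a causal link to treatment. The serious adverse event definition in protocol 9.1.3 applies "unless it meets the definition of a disease-related event as defined in" that section. Protocol 9.2.1 requires reporting of "all disease-related events observed by the investigator or reported by the subject that occur after first dose of IP through the EOS visit" or later.

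**Exposure.** Protocol 10.5.5 lists exposure to investigational product among the safety analyses and assigns those to the safety analysis set. SAP 10.7 reports safety data on that set by treatment actually received. SAP 10.7.5 instead uses the full analysis set by randomized group. Protocol 10.5.5.2, the specific exposure section, names neither set nor grouping.

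**eGFR.** SAP 6.6 gives the creatinine in the eGFR formula in mg/mL. SAP 10.4 summarises baseline eGFR in five bands: below 15, 15 to below 30, 30 to below 60, 60 to below 90, and 90 or more.

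**The concern.** The SAP is meant to detail the protocol's analyses, but on DREs it makes a planned table optional. In an osteoporosis trial that table is the planned place for ordinary fractures by arm, because the definitions normally keep them out of the AE and serious adverse event tables. With an undefined condition, whether a handful of fractures is compared between arms could be decided after the events are known. Listed events stay visible; what may be lost is the by-arm summary.

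The exposure rule could give the exposure and AE tables different denominators or arm assignments. The creatinine unit, if programmed as written, gives meaningless baseline eGFR values.

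**Working it through.** The plan states no figure on any of these points, so there is none to reproduce.

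**(a) How often would events occur but be too few to tabulate?**

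Inputs: 60 women (protocol 3.1); 6-month treatment period and 9 months in total (protocol 3.5.1). The documents give neither a fracture rate nor a threshold. I assume 1 to 6 fractures per 100 person-years, full follow-up and Poisson counts.

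- 6 months: 60 × 0.5 = 30 person-years; mean m = 0.3 to 1.8.
- 9 months: 60 × 0.75 = 45 person-years; m = 0.45 to 2.7.

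If the condition means at least 3 events, the case that matters is 1 or 2 events, with P = e^(−m) × (m + m²/2):

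- m = 0.3: 0.741 × 0.345 = 0.256
- m = 1.8: 0.165 × 3.42 = 0.565
- m = 0.45: 0.638 × 0.551 = 0.351
- m = 2.7: 0.0672 × 6.345 = 0.426
- maximum at m = √2 = 1.41: 0.587 (4.7 per 100 person-years over 6 months, 3.1 over 9 months)

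The range is therefore 26% to 59% over 6 months and 35% to 59% over 9 months.

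If it means at least 2 events, only a single event is left untabulated, with P = m × e^(−m): 0.222 at m = 0.3, 0.298 at 1.8, 0.287 at 0.45, 0.181 at 2.7, and a maximum of 0.368 at m = 1. That is 22% to 37% over 6 months and 18% to 37% over 9 months. If it means at least 1 event, nothing is lost.

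This counts events, whereas the protocol's table counts subjects. On the subject scale, assumed DRE risks of 1%, 2% and 5% give 0.6, 1.2 and 3.0 expected subjects among 60, and a 45%, 70% and 95% chance of at least one.

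**(b) Exposure.**

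Take an arm of 30 in which k subjects are never dosed and the rest receive all 6 doses (an assumption). The mean is 6.0 doses on the safety set and 6 × (30 − k)/30 on the full analysis set: 5.8, 5.6 and 5.4 for k = 1, 2 and 3. With k = 1, exposure has N = 30 and the AE tables N = 29. With k = 0 and no mis-dosing the two agree.

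**(c) eGFR.**

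For women in this trial the SAP 6.6 formula is eGFR = 175 × Scr^(−1.154) × Age^(−0.203) × 0.742. Entering the same creatinine in mg/mL rather than mg/dL divides Scr by 100 and multiplies eGFR by 100^1.154 = 203.2. Ages 55 to 90 come from the eligibility criteria; creatinine of 0.5 to 3.0 mg/dL is my assumption.

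| Creatinine, age | eGFR, entered as mg/dL | eGFR, entered as mg/mL |
|---|---|---|
| 0.5 mg/dL, 55 | 128 | 26,034 |
| 0.9 mg/dL, 70 | 61.9 | 12,580 |
| 3.0 mg/dL, 90 | 14.7 | 2,979 |

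Entered as mg/dL, the assumed range spans all five bands. Entered as mg/mL, everyone falls in the top band. Setting eGFR = 90 gives Scr = 0.679 at age 55 and 0.623 at age 90. Read as mg/mL, these are 67.9 and 62.3 mg/dL, so a subject would need creatinine above about 62 to 68 mg/dL to leave the top band. Four of the five bands would be empty.

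**The case against.** The case against concerns weight rather than fact. Neither fractures nor DREs are an endpoint, and no inferential safety testing is planned. With one or two events a listing shows each one, and if it carries treatment, the count by arm can be read off. Fractures that qualify as AEs are still tabulated, and adjudicated "atypical femoral fracture (AFF) will also be summarized as EOIs". The fracture rate and the threshold of 3 are assumptions, and the result depends heavily on them. All of this stands, and it is why the point is minor. It does not explain why the SAP makes conditional a table the protocol states unconditionally.

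The judgement of sufficiency could be made on a blinded pooled count. Protocol 10.3 keeps the study team blinded until formal unblinding, though it lets certain functions be unblinded earlier. So the documents neither show an unblinded decision nor rule one out.

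The statement that ordinary fractures stay out of the AE tables rests on the protocol's definitions. The SAP places DREs in the AE listing without saying whether they count in AE incidence. That qualification is fair, and the SAP should settle it.

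On exposure, SAP 10.7.5 is explicit, so a programmer faces no ambiguity, and dosing is in clinic within 72 hours of randomization, so undosed subjects should be rare. The conflict is only with the general rules. On eGFR, the unit is probably a typographical error, and the absurd values would be noticed. Neither document states mg/dL for creatinine; that correction is inferred from the bands and the assumed creatinine range.

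**Conclusion.** All three discrepancies are in the current text. The DRE condition is the substantive one: it weakens a protocol-stated table. Under the assumed rates there is a 26% to 59% chance over 6 months that fractures occur but go untabulated if the threshold is 3, and none if it is 1. The exposure mismatch has no numerical effect if everyone is dosed as randomized. The unit error is confined to one descriptive baseline summary, because eGFR is not a covariate in the BMD models.

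No efficacy analysis changes, and AE incidence is unaffected provided DREs are kept out of the AE tables as protocol 9.1.1 defines them. Overall the point is minor. Confidence is high in the textual mismatches; the size of (a) depends on the assumed rate and threshold.

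**What to change.** - **SAP 10.7.1:** remove the sufficiency condition. Tabulate DREs and fatal DREs by arm, system organ class and preferred term, at least for the 6-month treatment period; a 9-month table is optional. State that DREs shown in the AE listing are not counted in AE incidence unless they qualify as AEs. If a condition is kept, give the event count, fix it before any unblinding, and record it in SAP section 11 as a change from the protocol.
- **SAP 10.7.5:** summarise doses received and cumulative exposure on the safety analysis set by actual treatment. Days on study may stay on all randomized subjects.
- **SAP 6.6:** change mg/mL to mg/dL.

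The cost is three wording edits and one short table that may be nearly empty.
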